10.1.2.6.3. Vital signs, clinical examination and other observations related to safety

10.1.2.6.3.1. Vital signs and clinical examination

Vital signs and clinical examination will be described, in terms of value at baseline, value at each post-baseline visit under treatment and last post-baseline value under treatment; as well as in terms of change from baseline to each post baseline visit under treatment and to last post-baseline value under treatment.

10.1.2.6.3.2. Electrocardiogram

ECG parameters will be described, in terms of value at baseline, value at each post-baseline visit under treatment and last post-baseline value under treatment; as well as, for quantitative endpoints, in terms of change from baseline to each post baseline visit under treatment and to last post-baseline value under treatment. Moreover, values and changes from baseline of corrected QT interval will be described in classes, considering thresholds defined in ICH E14

(*i.e.*, ≤ 450 ,] 450; 480],] 480; 500] and > 500 ms for values, and ≤ 30 ,] 30; 60] and > 60 ms for changes).

10.1.2.7. Biomarkers analysis

Based on ctDNA, pharmacodynamic biomarkers, potential predictors of response as well as mechanisms of resistance could be explored. More details will be described in the SAP.

10.1.2.8. Interim analysis

There are 3 planned interim analyses: an early futility interim analysis (interim 0) will be triggered when ~ 83 PFS events have been observed in DN population which is designed under a hypothetical Phase 2 study that would have 95% power to detect a true hazard ratio for PFS of $HR \leq 0.525$ (assumptions of mPFS 4 months *versus* 2.1 months) with a one-sided alpha level of 0.10. This futility analysis will use both PFS and OS data to calculate the Predictive Probability of Success incorporating historical data based on an extension of the methodology proposed by Saint Hilary *et al.*⁴⁰ for decision making. More details on the methodology and PPos calculation will be provided in SAP. Study will be stopped for futility if the calculated PPos $< 10\%$. If the study proceeds, an interim OS analysis for futility (interim 1) will be conducted when approximately 33.3% of the planned final number of OS events in DN population (*i.e.* 128 of 383 OS events) have been observed. If the study proceeds, a second interim analysis will occur to evaluate futility and efficacy (interim 2) when 255 events (66.7% of the planned final number of OS events) have occurred in DN population.

10.2. Determination of sample size

Approximately 25 participants will be evaluated in Safety Lead-In part. The DMC will initially determine tolerability after 6 evaluable participants have been treated. If ≤ 2 participants out of the first 6 experience a DLT, and the DMC based on the totality of safety data determines the doses to be tolerable, then the Safety Lead-In will be expanded by an additional cohort of 6 participants. The DMC will again assess the tolerability when 12 participants have been enrolled and the 12th participant has completed the first treatment cycle. If ≤ 3 participants experience a DLT, and the DMC based on the totality of safety data determines the doses to be tolerable, the Safety Lead-In will be expanded to add another 13 participants, for a total of 25 participants. The DMC will meet again at the end of the Safety Lead-In part when approximately 25 participants have been treated.

The primary endpoint of Randomised part will be OS in DN population, the key secondary endpoint will be OS in TN population. The primary hypothesis will test whether treatment with trifluridine/tipiracil in combination with futuximab/modotuximab compared with trifluridine/tipiracil alone leads to OS prolongation in DN population. A total of 500 patients will be randomised in a 1:1 ratio to the 2 treatment arms and followed-up until at least 383 OS events are observed across the 2 treatment arms will provide 90% power to detect a true hazard ratio (HR) ≤ 0.71 (median OS: 8.5 *vs* 12 months) using a stratified log-rank test (stratified by Performance Status [PS] [0 *vs* 1], extracellular domain EGFR mutations [extracellular domain (ECD)] [presence *vs* absence] and previous regimens of treatment [2 *vs* ≥ 3]), with an overall 1-sided significance level of 0.025 for the primary endpoint (adjusted for OS interim analyses). Assuming enrolment over 21 months with a ramp-up to a maximum of 30 patients per month and a lost-to-follow-up rate of 7% across both treatment arms, the timing of the primary analysis is expected to be at 37.5 months after 1st randomisation.

To control type I and type II errors, the planned interim analyses for OS will utilise O'Brien Fleming alpha spending function (the Lan-DeMets method)⁴¹ for efficacy boundaries determination and Hwang-Shih-Decani (non-binding)⁴² beta spending function with γ parameter equal to -1.5 for futility boundary determination. If OS in DN population is significant at final analysis when 383 OS events have occurred in the DN population, OS in the TN population will be tested at the full alpha level, *i.e.*, 0.025. The OS testing plan for the primary endpoint has 90% power conditional on passing the early futility interim analysis (interim 0).

Since the boundary is dependent on the number of OS events, the actual boundary used will be re-calculated, incorporating the spending function as defined, based on the number of actual OS events analysed at the time of the interim analysis relative to the planned 383 events. The boundary for the final analysis will similarly be adjusted in accordance with the amount of remaining alpha. The interim analysis specifications per the plan are provided in Table (10.2) 1.

Table (10.2) 1 - Interim analysis specifications

Analysis	IF	# OS Events	Efficacy				Futility			
			Z _{boundary}	P _{boundary}	α spend	HR _{crit}	Z _{boundary}	P _{boundary}	β spend	HR _{crit}
Interim 1	0.334	128	NA	NA	NA	NA	-0.132	0.553	0.019	1.024
Interim 2	0.666	255	2.511	0.006	0.006	0.73	0.997	0.159	0.049	0.883
Final	1	383	1.993	0.023	0.025	0.816	1.993	0.023	0.1	0.816

IF = information fraction. Z_{boundary} is the critical test statistic value at which futility (< Z) or efficacy (> Z) would be concluded. P_{boundary} is the critical one-sided p-value threshold for the comparison (> p for futility, < p for efficacy). α spend and β spend are the amount of type I and type II error spent at each analysis, respectively. HR_{crit} is the observed hazard ratio threshold (> HR for futility, < HR for efficacy).

The DMC will be responsible for evaluating the interim futility and efficacy analysis and making a recommendation about early termination due to observed study results.

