4.4.3. Discontinuation of the study in the event of objective reached

An efficacy interim analysis is planned for the study when approximately 66% of the targeted total number of OS events have been reached. In case statistical significance is achieved at this planned interim analysis, the study will be stopped early for efficacy. Otherwise, the study will proceed to final analysis.

After having informed the International Coordinator, the sponsor or the DMC or the Institutional Review Board (IRB)/IEC or the Competent Authorities may terminate the study before its scheduled term. The IRB/IECs and competent authorities will be informed according to local regulations.

If the study is prematurely discontinued due to objective reached, the ongoing participants should be seen as soon as possible, and the assessments described in [Section 5.8](#) should be performed.

Under some circumstances, the investigator may be informed of additional procedures to be followed in order to ensure that adequate consideration is given to the protection of the participant's interests.

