- The distribution of OS will be compared between the two treatment groups using a stratified log-rank test at one-sided 2.5% level of significance (stratification factors based on IWRS data).
- OS for each arm will be summarized using Kaplan Meier curves and further characterised in terms of the median and survival probabilities at 6, 12 and 18 months along with the corresponding 2-sided 95% CI for the estimates.
- The hazard ratio of OS with its 95% confidence interval will be estimated with a stratified Cox proportional hazard model (stratification factors based on IWRS data).

As OS in TN population is identified as the key secondary estimand, closed sequential testing procedure will be used to statistically evaluate and interpret OS in TN population only if the

primary estimand, OS in DN population, is statistically significant. Therefore, the family-wise error rate is strongly controlled.

The following analyses will be done as sensitivity analyses:

- The proportional hazards assumption will be checked. If relevant, other statistical method could be used.
- OS analysis based on PPS.

Other sensitivity analyses will be defined in the SAP if necessary.

For missing data (not linked to intercurrent events), *i.e.* participants without documentation of death (lost to follow-up, withdrawal of consent, administrative end of study), the OS will be censored on the last contact date the participant was known to be alive or the cut-off date, whichever is earlier.

The same subgroup analyses as used for the primary estimand will be done.

10.1.2.4.2.3. Supplementary estimand based on OS

One supplementary estimand based on OS is defined in order to assess the effect of the randomised treatments on the survival time in all subjects who are KRAS/NRAS and BRAF WT (Double negative [DN]) before participants receive further anti-cancer therapy (while on treatment strategy).

The other estimand based on OS is defined in order to assess the effect of the randomised treatments on the survival time in all subjects who are KRAS/NRAS, BRAF WT and EGFR-extracellular domain WT (Triple negative [TN]) before participants receive further anti-cancer therapy (while on treatment strategy).

The aim of this estimand is to evaluate the effect of the study treatment without a potential effect of another therapy.

The use of data post intercurrent events will be different according to the IE:

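### No rule covers the TN key secondary test if the trial stops for efficacy at interim 2, which is where about two thirds of DN wins fall at the design hazard ratio

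*Protocol*

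**What the plan says.** Protocol Section 10.2 sets DN OS as the primary endpoint "with an overall 1-sided significance level of 0.025 for the primary endpoint (adjusted for OS interim analyses"). Table (10.2) 1 gives efficacy boundaries of z = 2.511 at interim 2 (255 DN deaths) and z = 1.993 at the final analysis (383 DN deaths). It has no TN column.

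The same section makes the TN test conditional on DN being significant at the final analysis, when 383 DN deaths have occurred. In that event "OS in the TN population will be tested at the full alpha level", given as 0.025.

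Section 4.4.3 covers a DN success at interim 2: "In case statistical significance is achieved at this planned interim analysis, the study will be stopped early for efficacy". The study goes on to the final analysis only if that does not happen.

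Section 10.1.2.4.2.2 tests TN at one-sided 2.5% if DN is significant, without naming the look, and concludes: "Therefore, the family-wise error rate is strongly controlled".

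SAP Section 1 records that the Randomised part was cancelled and refers to the protocol for everything about it.

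**The concern.** The TN rule is tied to an analysis that does not take place when the trial succeeds early. Section 10.2 gives TN one test at 383 events, while Section 4.4.3 ends the study at 255 events if DN crosses. A sponsor following the text would have no pre-specified TN test after an early win, and TN OS is the only key secondary endpoint. Someone filling the gap from Section 10.1.2.4.2.2 could test TN at 0.025 at the interim, and that choice would undo the error control the section claims. What is at stake is either a confirmatory claim lost by omission or one made at an unplanned error rate.

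**Working it through.** **Inputs (Protocol Sections 10.1.2.8 and 10.2).** Looks at 128, 255 and 383 DN deaths; 1:1 allocation; overall one-sided alpha 0.025; Lan-DeMets O'Brien-Fleming spending; non-binding futility at z = -0.132 and 0.997; and "90% power to detect a true hazard ratio (HR) ≤ 0.71".

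**Step 1: reproduce the plan's figures.**
- Information fraction t = 255/383 = 0.666.
- Alpha spent at interim 2 = 2[1 - Φ(2.2414/√0.666)] = 0.0060, so z = 2.511. The final boundary is z = 1.993, p = 0.023.
- Critical HR = exp(-2z/√events): exp(-2×2.511/√255) = 0.730 and exp(-2×1.993/√383) = 0.816.
- Power with futility obeyed is 0.896 at HR 0.71 and 0.900 at HR 8.5/12 = 0.7083.

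All agree with the protocol.

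**Step 2: how often the literal rule leaves TN untested.** At HR 0.71 the mean of Z at interim 2 is √(255/4) × ln(1/0.71) = 7.984 × 0.3425 = 2.73. So P(Z > 2.511) = Φ(0.22) = 0.588. The probability of a first DN win at the final analysis is 0.308 with futility obeyed (0.327 without). The share of DN wins at interim 2 is 0.588/(0.588 + 0.308) = 66% (64% without futility).

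| True DN HR | Efficacy stop at interim 2 | DN win at final | Share of wins at interim 2 |
|---|---|---|---|
| 0.65 | 0.82 | 0.16 | 84% |
| 0.71 | 0.59 | 0.31 | 66% |
| 0.73 | 0.50 | 0.34 | 59% |
| 0.75 | 0.41 | 0.36 | 54% |
| 0.80 | 0.23 | 0.32 | 42% |

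Most DN wins come at interim 2 only for a true HR below about 0.76.

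**Step 3: TN type I error.** The documents do not give the TN share of deaths, f, so it is assumed to lie between 0.5 and 0.98. TN is nested in DN, so the two log-rank statistics at the same look have correlation √f. The TN information fraction is taken equal to that of DN. TN has no effect, the DN effect is varied to find the worst case, and futility is ignored because it is non-binding.

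| f | Literal: TN at final only, z 1.96 | TN at z 1.96 at the look where DN crosses | TN with own boundary, 2.511/1.993 |
|---|---|---|---|
| 0.5 | 0.012 | 0.028 | 0.015 |
| 0.7 | 0.013 | 0.030 | 0.017 |
| 0.8 | 0.015 | 0.031 | 0.018 |
| 0.9 | 0.016 | 0.033 | 0.020 |
| 0.95 | 0.017 | 0.035 | 0.022 |
| 0.98 | 0.019 | 0.036 | 0.023 |

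The maxima in the middle column occur at a DN HR of about 0.82 to 0.93. With DN HR 0.71 and no TN effect, the error in that column is about 0.025.

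**Step 4: chance of a TN win if HR is 0.71 in TN as well** (TN drift = √f × DN drift, futility ignored).

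| f | Literal rule | Own boundary at either look |
|---|---|---|
| 0.7 | 0.24 | 0.61 |
| 0.8 | 0.27 | 0.71 |
| 0.9 | 0.295 | 0.80 |

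**The case against.** The best defence is that the written rule is valid. Section 10.2 is the only text that times the TN test. One test at one pre-specified analysis, after DN has succeeded, needs no spending function, and its error is at most 0.019 in the table above. This stands. A reader might infer that the strong-control statement is false; the protocol as written does not support that. It would become false only if the silence of Section 10.1.2.4.2.2 on timing were used to test TN at 0.025 at interim 2. Nor does any text allow TN to be tested at both looks: DN crossing at interim 2 ends the study, and without a DN crossing TN is not tested there.

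The worst-case figures for that unwritten rule also need care. With f = 0.95, a DN HR of 0.912 with no TN effect implies an HR of about exp(ln 0.912/0.05) = 0.16 in EGFR-ECD-mutated participants, which is extreme. With f = 0.7 the implied HR is about 0.62, and the worst case is still 3.0%.

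It is also fair to say that the loss depends on the true effect. At HR 0.80 the interim stop probability is only 23%. TN hazard ratios and Kaplan-Meier estimates would still be reported after an early stop, so what is lost is the formal claim.

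Finally, the current SAP dropped all randomised-part methods on cancellation, so a TN interim rule may have stood in SAP version 1.0. That cannot be checked here. The protocol would still need to agree with it, since Section 10.2 names the final analysis only.

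**Conclusion.** The gap is real, and it costs power rather than validity. Under the protocol's own boundaries and design HR of 0.71, the key secondary endpoint goes formally untested in 59% of trials, about 66% of those that win on DN. These figures need no assumption about TN. The drop in the chance of a TN win (0.24-0.30 against 0.61-0.80) assumes a TN share of deaths of 0.7 to 0.9, equal information fractions and a TN HR of 0.71. The 2.8% to 3.6% error applies only to a rule the protocol does not state; it shows why the gap should not be filled by testing at 0.025 at the interim. With the Randomised part cancelled, the point concerns the protocol design and any reuse of it.

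**What to change.** In Sections 10.1.2.4.2.2 and 10.2, state that once DN is significant, at interim 2 or at the final analysis, TN is tested at that same look against its own Lan-DeMets O'Brien-Fleming boundary at overall one-sided 0.025, computed on TN events. This replaces the final-only test at the full 0.025. Give the planned number of TN events so that the boundary can be calculated.

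The cost is about two sentences and no extra participants. The TN threshold at the final analysis becomes slightly stricter, z = 1.993 instead of 1.96 if the TN information fraction matches that of DN. In return, TN is tested after an early stop, worst-case TN error stays at or below about 0.023, and the strong-control statement holds whichever look DN crosses.

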10.3. Pharmacokinetic analyses and PK/PD analysis

10.3.1. Safety Lead-In part

In order to inspect the pharmacokinetic profiles of futuximab/modotuximab and trifluridine/tipiracil when given in combination, external Visual Predictive Check on the individual serum for futuximab/modotuximab and plasma for trifluridine/tipiracil concentrations will be performed. For this, previously developed population PK models for futuximab/modotuximab, and trifluridine/tipiracil, will be used to perform simulations (1000 replicates) of the expected concentration-time profile of these compounds administered as monotherapies. The [P5; P95] prediction interval (*i.e.* encompassing 90% of overall predicted concentrations) and the median of the overall simulated plasma/serum concentration-time curves will be calculated and will be graphically superimposed with observed concentration-time data.

10.3.2. Randomised Part

Concentrations of futuximab/modotuximab and trifluridine/tipiracil will be analysed by a population modelling approach, described in a separated Data Analysis Plan (DAP). This analysis will provide pharmacokinetic parameters (such as Cmax and AUC) and their associated variability in participants and will be the object of a separate report. Interim analyses using this approach could be performed if required.

Exploratory assessment of the relationship between exposure and pharmacodynamics (as safety and efficacy) will be performed and if applicable, population pharmacokinetic-pharmacodynamic (PK/PD) models will be developed and a DAP will be set

up and reported separately. The pharmacometrics analysis may require other model-based approaches to better describe the PK/PD of the compound. In this case a description of these methods would be included in a specific DAP.

The data of the present study could be pooled with data from previous or future clinical studies, if relevant. It could also be combined with literature data if required.

11. DIRECT ACCESS TO SOURCE DATA/DOCUMENTS

The investigator will allow the monitors, the persons responsible for the audit, the representatives of the IRB/IEC, and of the Competent Authorities to have direct access to source data / documents.

12. QUALITY CONTROL AND QUALITY ASSURANCE

12.1. Study monitoring

Clinical site monitoring is conducted to ensure that the rights and well-being of human subjects are protected, that the reported trial data are accurate, complete, and verifiable, and that the conduct of the trial is in compliance with the currently approved protocol/amendment(s), with GCP, and with applicable regulatory requirement(s).

Monitoring for this study will be performed by the structure mentioned in document entitled Administrative part of clinical study protocol.

If on-site monitoring cannot be accomplished, remote Source Data Verification may be performed in accordance with local regulations

Details of clinical site monitoring are documented in a Clinical Monitoring Plan (CMP). The CMP describes in detail who will conduct the monitoring, at what frequency monitoring will be done, at what level of detail monitoring will be performed, and the distribution of monitoring reports.

12.1.1. Before the study

The investigator will allow the monitor to visit the site and facilities where the study will take place to ensure compliance with the protocol requirements.

Training sessions may be organised for the investigators and/or instruction manuals may be given to the investigators.

12.1.2. During the study

The investigator will allow the monitor to:

- Review of the study site's processes and procedures.
- Verify appropriate clinical investigator supervision of study site staff and third-party vendors.
- Inspect the site, the facilities and the material used for the study.
- Meet all members of his/her team involved in the study.
- Consult the documents relevant to the study.

- Have access to the e-CRF (*i.e.* Access to an analogic phone line or his/her computer) and/or to the e-PRO service provider's database to check that they been filled out correctly.
- Check that the e-CRF and e-PRO have been filled out correctly.
- Directly access source documents for comparison of data therein with the data in the electronic case report forms and/or to the e-PRO/e-COA service provider's database.
- Verify that the study is carried out in compliance with the protocol and local regulatory requirements.

The study monitoring will be carried out at regular intervals, depending on the recruitment rate and / or the investigation schedule, and arranged between the investigator and monitor.

All information dealt with during these visits will be treated as strictly confidential.

12.2. Computerised medical file

If computerised medical files are used, and if the computer system allows, no change made in the medical files by the investigator should obscure the original information. The record must clearly indicate that a change was made and clearly provide a means to locate and read the prior information (*i.e.* audit trail). The investigator will save data at regular intervals.

The investigator must guarantee the integrity of the study data in the medical files by implementing security measures to prevent unauthorised access to the data and to the computer system.

If the computerised medical files are considered as not validated by the sponsor, the investigator undertakes:

- At the start of the study, to print the medical files of all participants allowing a reliable verification of the study criteria (*e.g.* Medical history/previous treatments/ characteristics of the studied disease documented within the period of time defined by the study protocol).
- During the study, to print in real time each data entry and each data change.

The investigator or designated person of the site team will personally sign, date and give the number of pages on the first or last page of each print-out. At each visit by the monitor, the investigator will provide all the print-outs of the medical files of the participants. The monitor will personally sign and date the first (or last) page then initial all pages in each paper print-out.

If the computer system allows the tracking of the changes made to the medical files, the investigator will supply the monitor, at each visit, with a print-out of the medical files of the participants and the records of the changes made. Each print-out will be personally dated and signed, by the investigator and the monitor on the first page. The number of pages will also be indicated by the investigator and the monitor on the first page.

If the computerised medical files are considered as validated by the sponsor, the investigator undertakes to give access to the monitor to the computerised medical files of all participants. If the monitor cannot access to the tracking of the changes made to the medical files, the investigator will supply the monitor, at each visit, with a print-out of the records of the changes made to the medical files of the participants. Each print-out will be personally dated and signed, by the investigator and the monitor on the first page. The number of pages will also be indicated by the investigator and the monitor on the first page.

The investigator undertakes to keep:

- All medical file print-outs signed and dated by him/her and by the monitor when the computer system is considered as not validated by the sponsor.
- If the computer system used allows changes to be made, the print-outs of the audit trail when the computer system is considered as not validated by the sponsor or when the monitor cannot access to the audit trail in the computer system.
- All original source-documents (originals of specific examinations, informed consent forms, therapeutic unit tracking form...).

